1.5. Rationale for Selection of BGB-290 Dose

Based upon the overall safety, efficacy, and PK profile of BGB-290, the dose of BGB-290 60 mg PO BID was selected using available clinical data from Study BGB-290-AU-002 (Section 1.4.2.3). The study determined the MTD of BGB-290 to be 80 mg PO BID (160 mg/day). The dose of 60 mg BID was selected for further evaluation based on the following findings (refer to the [BGB-290 Investigator's Brochure](#)):

- A linear PK profile observed up to 80 mg BID
- Similar toxicity profiles at 60 mg and 80 mg BID with the following exceptions:
 - Fewer patients at 60 mg BID experienced treatment-related TEAEs of anemia and neutropenia.
 - There was a slightly higher rate of dose interruptions at 80 mg vs 60 mg BID for anemia and nausea.
- Responses were observed across the dose range evaluated

1.6. Study Rationale

Inoperable locally advanced and metastatic gastric cancer continues to be an incurable disease with 5-year survival rates below 10% despite various available treatment regimens, necessitating the exploration of additional and different therapeutic approaches. First-line platinum-based therapy can result in response rates around 30% to 50%. Treatment with a platinum doublet or triplet, however, typically does not last longer than 6 months due to accumulating chemotherapy toxicities, and there is no evidence that further treatment with a fluoropyrimidine as single agent provides clinical benefit. The time point of maximum tumor response to platinum-based therapy provides a unique opportunity to further improve on clinical benefit rather than wait for PD and initiation of second-line therapy.

PARP inhibitors, in general, have favorable attributes that make them an interesting drug class for maintenance therapy as they are oral agents and tolerated well, in particular when compared with first- or second-line chemotherapy. BGB-290 is a promising PARP inhibitor to study in the gastric

cancer maintenance setting as it is a potent and selective inhibitor of PARP1 and PARP2. It has excellent PARP trapping activity that is likely to be more important for antitumor activity than catalytic PARP inhibition. In the clinic, BGB-290 has shown favorable PK properties, has been tolerated well, and has achieved maximum pharmacodynamic target modulation in PBMCs at a dose level well below the recommended Phase 2 dose (10 versus 60 mg BID).

The rationale for developing the PARP inhibitor BGB-290 in gastric cancer is several fold. The biology of gastric cancer indicates that a large subset of these tumors should be sensitive to PARP inhibition because of abnormalities that have been linked to PARP inhibitor sensitivity in various tumor types. This includes CIN and evidence of HRD, such as loss of ATM expression or BRCA mutational signatures. There is a significant overlap between cancers with platinum sensitivity and biomarkers for PARP inhibitors. Furthermore, activity of PARP inhibitors is not limited to biomarker-positive cancers but also includes biomarker-negative cancers with demonstrated platinum sensitivity. Gastric cancer is a cancer type for which platinum sensitivity has been clearly established, predicting that PARP inhibitors may have significant activity in patients with a CR or PR. Finally, other PARP inhibitors have shown activity in gastric cancer, particularly in cases with loss of ATM.

In summary, BGB-290 is an excellent candidate to determine the effects of PARP inhibition in this unmet medical need of patients with platinum-sensitive disease, as demonstrated by a CR or PR, but have no further treatment options to consolidate or maintain the clinical benefit derived from first-line chemotherapy.

1.7. Risk-Benefit Assessment

BGB-290 has been studied in nonclinical toxicity and Phase 1 clinical studies. BGB-290 toxicities are largely consistent with the safety profile shared by other PARP inhibitors.

MDS and AML have been reported in a small number (< 1%) of patients treated with PARP inhibitors, especially in patients harboring a germline BRCA mutation ([Ricks et al, 2015](#)). Typically, patients who develop MDS and AML while on therapy with a PARP inhibitor have a history of extensive previous chemotherapy and some have a history of previous cancer or bone marrow abnormalities. To date, there have been no reports of MDS or AML in patients treated with BGB-290. Patients in this study will be monitored monthly for hematological toxicities and events of MDS and AML will be reported as SAEs irrespective of time elapsed since end of study treatment.

Given that patients with advanced gastric cancer currently have no treatment options after completion of first-line therapy, the risk of BGB-290 toxicities appears acceptable considering the strong rationale for exploring PARP inhibition in the maintenance setting.

1.8. Study Conduct

This study will be conducted in compliance with the protocol approved by the Institutional Review Board (IRB) or Independent Ethics Committee (IEC) and Regulatory Authorities and in accordance with Good Clinical Practice (GCP) standards.

2. STUDY OBJECTIVES

2.1. Primary Objective

- To evaluate the efficacy of maintenance therapy with BGB-290 versus placebo in patients with inoperable locally advanced or metastatic gastric cancer with a CR or confirmed PR after first-line platinum-based chemotherapy, as measured by:
 - PFS by investigator assessment

2.2. Secondary Objectives

- To further evaluate the efficacy of maintenance therapy with BGB-290 versus placebo in patients with inoperable locally advanced or metastatic gastric cancer with a CR or confirmed PR after first-line platinum-based chemotherapy, as measured by:
 - OS
 - Time to second subsequent treatment (TSST) by investigator assessment
 - ORR (CR or PR) by investigator assessment
 - Duration of response by investigator assessment
 - Time to response by investigator assessment
- To evaluate safety and tolerability of BGB-290 versus placebo, as measured by:
 - Incidence, timing, and severity of treatment-emergent adverse events (TEAEs), graded according to National Cancer Institute-Common Terminology Criteria for Adverse Events (NCI-CTCAE) Version 4.03

2.3. Exploratory Objectives

- To confirm the PK of BGB-290, as measured by:
 - Lowest observed plasma concentrations (C_{trough}) at steady-state and other PK parameters for patients who received BGB-290
- To assess patient-reported outcomes on health-related quality of life, as measured by:
 - European Quality of Life 5-Dimensions 5-Levels Health Questionnaire (EQ-5D-5L)
 - European Organisation for Research and Treatment of Cancer Quality of Life Cancer Questionnaire (EORTC QLQ-C30)
 - EORTC QLQ gastric cancer module (EORTC QLQ-STO22)
- To explore potential biomarkers associated with the pharmacodynamics, response, and resistance to BGB-290:
 - Including, but not limited to, expression and mutations of genes in the DNA damage response pathway, LOH, and relationship to efficacy and resistance to BGB-290

3. STUDY DESIGN

3.1. Summary of Study Design

This is a double-blind, placebo-controlled, randomized, multicenter, global Phase 2 study comparing the efficacy and safety of single-agent poly (ADP-ribose) polymerase (PARP) inhibitor BGB-290 to placebo as maintenance therapy in patients with advanced gastric cancer who have completed first-line platinum-based chemotherapy.

To be eligible for participation in the study, patients must have histologically confirmed adenocarcinoma of the stomach or gastroesophageal junction with inoperable locally advanced or metastatic disease. Patients must have achieved a PR that is maintained for ≥ 4 weeks or a CR as determined by the investigator according to Response Evaluation Criteria in Solid Tumors (RECIST) Version 1.1 with platinum-based first-line chemotherapy. The primary endpoint of the study is PFS by investigator assessment. Sufficient tumor tissue (archival biopsy) must be provided for central laboratory determination of HRD status for randomization and exploratory biomarker analyses.

Patients will be randomized ≤ 8 weeks after the last platinum dose of first-line chemotherapy. Cycles will be 28 days in length. Once the treatment phase has been completed, an end of treatment (EOT) visit should occur with subsequent phases of safety and long-term follow-up.

Central randomization (1:1) will be used to assign eligible patients to 1 of the following 2 arms.

Arm A: BGB-290 60 mg PO BID

Arm B: Placebo 60 mg PO BID

Patient randomization will be stratified by HRD status (LOH_{high} versus LOH_{low} versus unknown), region (China/Hong Kong/Taiwan versus Australia/Europe/North America versus Japan/South Korea versus rest of world [ROW]), and Eastern Cooperative Oncology Group (ECOG) performance status (0 versus 1).

Safety assessments will occur on Day 1 of each cycle, on Day 15 of Cycles 1 and 2, and as needed. Dose modifications will be made as outlined in Section 6.1.4. AEs will be followed and documented during the treatment period and for approximately 30 days after last study drug or until initiation of new anticancer therapy, whichever occurs first (Section 9 and Appendix 1). AEs will be graded according to NCI-CTCAE Version 4.03. An external independent data monitoring committee (IDMC) will periodically review safety data.

To confirm PK properties of BGB-290, blood samples will be taken at various time points as outlined in Section 7.6 and Appendix 1. Additionally, tumor tissue and blood samples will be obtained (as outlined in Section 7.7 and Appendix 1) to explore biomarkers of pharmacodynamics, response, and resistance to BGB-290 in gastric cancer.

Disease status will be assessed by the investigator using RECIST Version 1.1 (Appendix 2). Patients will undergo tumor assessments at screening and then every 8 weeks (± 7 days), or as clinically indicated.

There is no fixed duration of treatment.

[figure not shown]
Administration of BGB-290 or placebo will continue until PD, unacceptable toxicity, death, or another discontinuation criterion is met (Sections 5.5 and 5.7). Once the treatment phase has been completed, an EOT visit should occur within 7 days of stopping BGB-290 or placebo with subsequent phases of safety and long-term follow-up.

Long-term follow-up will include tumor assessments every 8 weeks (± 7 days) for those patients without PD, survival status, new anticancer therapy, and diagnosis of MDS or AML. Long-term follow-up will continue until the patient dies or another criterion for discontinuation from study is met (Section 5.7).

Once the study is completed and the study results are available, this study will be unblinded. For patients who have received BGB-290, the sponsor will continue providing the drug either on this study or through other options, ie, a roll-over study. Subjects who are on the Placebo arm will discontinue the study treatment.

Study procedures and assessments are detailed in Section 7 and Appendix 1. The study schema is provided in Figure 4.

Figure 4: Study Schema

Abbreviations: AML, acute myeloid leukemia; BID, twice daily; CR, complete response; ECOG, Eastern Cooperative Oncology Group; LOH, loss of heterozygosity; HRD, homologous recombination deficiency; MDS, myelodysplastic syndrome; PD, progressive disease; PO, oral; PR, partial response; q8w, every 8 weeks; ROW, rest of world; vs, versus.

Note: Key assessments during treatment phase: tumor assessments and patient-reported outcomes every 8 weeks, adverse events, hematology, and chemistry every 4 weeks. BGB-290 and placebo are to be administered continuously.

3.2. Independent Data Monitoring Committee

Regular safety monitoring (at least every 6 months) and efficacy monitoring will be performed by an IDMC. The IDMC will review SAE reports for the first 40 patients enrolled in the study and review aggregate safety data approximately 3 months after the 40th patient started on study drug to assess the benefit/risk. The IDMC may recommend study modification including termination of the study due to safety and/or efficacy concerns. The function and membership of the IDMC will be described in the IDMC charter.

In addition to the planned IDMC review(s), ad hoc reviews may take place based on new information.

Following IDMC review and discussion, the sponsor will make all final decisions regarding any change in study conduct. Please see the details in the IDMC charter.

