This is a double-blind, placebo-controlled, randomized, multicenter, global Phase 2 study comparing the efficacy and safety of single-agent poly (ADP-ribose) polymerase (PARP) inhibitor BGB-290 to placebo as maintenance therapy in patients with advanced gastric cancer who have completed first-line platinum-based chemotherapy.

To be eligible for participation in the study, patients must have histologically confirmed adenocarcinoma of the stomach or gastroesophageal junction with inoperable locally advanced or metastatic disease. Patients must have achieved a PR that is maintained for ≥ 4 weeks or a CR as determined by the investigator according to Response Evaluation Criteria in Solid Tumors (RECIST) Version 1.1 with platinum-based first-line chemotherapy. The primary endpoint of the study is PFS by investigator assessment. Sufficient tumor tissue (archival biopsy) must be provided for central laboratory determination of homologous recombination deficiency (HRD) status for randomization and exploratory biomarker analyses.

Patients will be randomized ≤ 8 weeks after the last platinum dose of first-line chemotherapy. Central interactive response technology will be used to randomize patients in a 1:1 ratio and assign eligible patients to 1 of 2 arms: Arm A – BGB-290 or Arm B – Placebo. Patient randomization will be stratified by HRD status (LOH_{high} versus LOH_{low} versus unknown), region (China/Hong Kong/Taiwan versus Australia/Europe/North America versus Japan/South Korea versus rest of world [ROW]), and Eastern Cooperative Oncology Group (ECOG) performance status (0 versus 1).

Cycles will be 28 days in length.

Safety assessments will occur on Day 1 of each cycle, on Day 15 of Cycles 1 and 2, and as needed. Dose modifications will be made if appropriate. Adverse events (AEs) will be followed and documented during the treatment period and for approximately 30 days after the last dose of study drug or until initiation of new anticancer therapy, whichever occurs first. AEs will be graded according to NCI-CTCAE Version 4.03. An external independent data monitoring committee will periodically review safety data.

[figure not shown]
To confirm PK properties of BGB-290, blood samples will be taken at various time points.

Additionally, tumor tissue and blood samples will be obtained to explore biomarkers of pharmacodynamics, response, and resistance to BGB-290 in gastric cancer.

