5 SAMPLE SIZE CONSIDERATIONS

This study is designed to provide 80% power for PFS. The following assumptions are used in determining the sample size for this study:

- Overall type I error rate: 0.1 (1-sided)
- Randomization: 1:1
- Median PFS for placebo group: 6.0 months
- PFS hazard ratio (HR; pamiparib/placebo): 0.63

A sample size of approximately 128 patients (64 per treatment group) is required to achieve 85 PFS events within the planned study duration of approximately 26 months after the first patient is randomized to study, assuming an estimated accrual period of 20 months.

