6.4 EFFICACY ANALYSIS

6.4.1 Primary Efficacy Analysis

Progression-Free Survival (PFS)

PFS is defined as the time from randomization date to disease progression per RECIST Version 1.1 by investigator assessment or death, whichever occurs first.

The final PFS analysis will be performed when 85 PFS events have occurred. The final PFS analysis will include all PFS events up to the date of data cutoff which is pre-defined based on the projected 85 PFS events on the blinded manner. A stratified 1-sided log-rank test at a 0.1 significance level incorporating the randomized stratification factors will be used to compare the distribution of PFS between pamiparib (Arm A) and placebo (Arm B).

The null and alternative hypotheses for the final PFS analysis are as follows:

H_0 : hazard ratio [HR] (pamiparib/placebo) = 1

H_a : hazard ratio [HR] (pamiparib/placebo) < 1

The treatment effect will be estimated by fitting a Cox Proportional Hazards model to the PFS including treatment arm as a factor and stratification factors (region, ECOG performance status) as strata. From this model, the HR will be estimated and presented with a 2-sided 95% CI.

The median and other quartiles of PFS for each treatment group will be estimated using the Kaplan-Meier method, and the 2-sided 95% CI will be calculated using the Brookmeyer-Crowley method (Brookmeyer and Crowley, 1982). The point estimate of PFS rates and the corresponding 95% CIs at selected landmark points (every three months up to 24 months) will be provided based on the Greenwood's estimate of the variance (Greenwood 1926). Kaplan-Meier curves for PFS will also be generated and plotted over time to provide a visual description of the PFS change over time. Primary efficacy analysis will be conducted by using the ITT Analysis Set.

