7 INTERIM ANALYSIS

No interim analysis is considered in this study.

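### Does the IDMC's efficacy monitoring in Protocol 3.2 undermine the single final PFS test when the SAP plans no interim analysis?

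*Protocol*

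**What the plan says.** **Committee remit, detailed section.** Protocol 3.2 states: "Regular safety monitoring (at least every 6 months) and efficacy monitoring will be performed by an IDMC". It continues: "The IDMC may recommend study modification including termination of the study due to safety and/or efficacy concerns". The one aggregate review it dates is to "review aggregate safety data approximately 3 months after the 40th patient started on study drug to assess the benefit/risk". It allows ad hoc reviews, sends function, membership and details to an IDMC charter, and leaves all final decisions on study conduct to the sponsor.

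**Committee remit, summaries.** The synopsis says "An external independent data monitoring committee will periodically review safety data". Protocol 3.1 says the same: "An external independent data monitoring committee (IDMC) will periodically review safety data". Neither sentence mentions efficacy.

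**Analysis plan.** SAP 7 reads: "No interim analysis is considered in this study". SAP 6.4.1 says "The final PFS analysis will be performed when 85 PFS events have occurred" and tests at 1-sided 0.1. SAP 6.2.5 makes no multiplicity adjustment. SAP 8, which lists departures from the protocol, does not mention IDMC efficacy monitoring.

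**The concern.** Taken together, these places seem to disagree. The synopsis and Protocol 3.1 describe a committee that reviews safety. Protocol 3.2 adds efficacy, with no endpoint, timing, boundary or direction. The SAP is written as if nobody looks at comparative PFS before the end.

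The primary test reserves no alpha for earlier looks. If the trial could stop for benefit on an early comparison, with the final test still at 0.1, the overall type I error would exceed 0.1. If it could stop for apparent lack of benefit, some trials of an effective drug would end early and power would fall below 80%. A reader with only these two documents cannot see which use of efficacy data, if any, the committee is allowed.

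**Working it through.** **1. Reproduce the plan's figure.** Inputs (Protocol 10.7, SAP 5): HR 0.63, 1-sided alpha 0.1, power 80%, 1:1 allocation.

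- Schoenfeld events = 4 × (1.2816 + 0.8416)² / (ln 0.63)² = 4 × 4.508 / 0.2135 = 84.5, rounded up to **85**.
- Power at 85 events = Φ(0.462 × √85 / 2 − 1.2816) = Φ(2.130 − 1.2816) = **0.802**.

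The stated 85 events and 80% power are those of a design with one analysis, which is what SAP 7 describes. No stated figure is wrong.

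**2. Can the passages be read together?**

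| Place | On efficacy | Conflict with SAP 7? |
|---|---|---|
| Synopsis, Protocol 3.1 | Silent; neither says safety only | No |
| Protocol 3.2, first sentence | Efficacy monitoring; the 6-month interval is attached to safety | Only if monitoring means a formal test |
| Protocol 3.2, dated review | Safety data, to judge benefit-risk | No |
| Protocol 3.2, termination | Advisory, over concerns | Only if acted on as a stopping rule |

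A committee that sees efficacy data as context for benefit-risk, with no hypothesis test, is not conducting an interim analysis. SAP 1 also says its focus is the planned final analysis, so it need not describe committee practice.

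**3. What it would take to do harm.** The documents give no efficacy looks, so everything here is assumed: exponential PFS with placebo median 6.0 months, 128 patients, uniform accrual over 20 months, no dropout, looks at the months shown, final test at 1-sided 0.1 with 85 events. Expected events at months 6, 12 and 18 are 10.7, 35.3 and 66.7 under HR 1, and 9.0, 30.4 and 58.9 under HR 0.63. The log-rank Z was simulated with independent increments (2,000,000 paths per scenario).

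Stopping for lack of benefit:

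| Looks (month) | Type I error, stop if HR>1 | Power, stop if HR>1 | Power, stop if HR>1.25 |
|---|---|---|---|
| 18 | 0.100 | 0.800 | 0.802 |
| 12, 18 | 0.092 | 0.76 | 0.794 |
| 6, 12, 18 | 0.071 | 0.62 | 0.70 |

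Type I error when stopping for benefit at the early threshold shown:

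| Looks (month) | p<0.001 | p<0.01 | p<0.05 | p<0.1 |
|---|---|---|---|---|
| 18 | 0.100 | 0.100 | 0.108 | 0.133 |
| 12, 18 | 0.100 | 0.103 | 0.130 | 0.178 |
| 6, 12, 18 | 0.101 | 0.109 | 0.159 | 0.232 |

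**4. Reading the tables.** Late looks or strict thresholds leave 0.1 and 80% essentially intact. The worst entries need either a stop on an observed HR above 1 at about 9 events, or a stop for benefit at nominal 0.1 at every look. Neither document suggests such a rule. The month 6, 12 and 18 schedule itself borrows an interval that Protocol 3.2 gives for safety monitoring.

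**The case for a change.** The strongest case for a change is that Protocol 3.2 does assign efficacy monitoring, does name efficacy as a ground for recommending termination, and does not rule out stopping for benefit. SAP 8 lists the departures from the protocol and never withdraws that duty. The charter does not settle the matter: an efficacy stopping rule there would contradict SAP 7, and without one the wording in 3.2 has nothing behind it. Because the sponsor has the final say, it could act on an efficacy recommendation with no stated rule. A sentence or two would close the gap without touching the sample size.

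What stands is that the remit is loosely worded and that these documents alone do not show which efficacy data the committee sees. What does not stand is that the error rates hold only if nobody acts on efficacy before 85 events: a month-18 look that stops on HR>1 leaves alpha at 0.100 and power at 0.800. Nor do the synopsis and Protocol 3.1 contradict 3.2; a summary that leaves out a detail does not deny it. The clarifying sentence would mostly record what is already implied: the committee recommends, the sponsor decides, there is no interim analysis, and there is one test at 85 events.

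**Conclusion.** No change to the plan is called for. This is a gap in description that a competent committee and analyst would fill sensibly from what is written: any efficacy information serves benefit-risk judgement, and PFS is tested once, at 85 events, at 1-sided 0.1. Followed that way, the plan has its stated type I error and a power of 0.802.

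The natural reading of efficacy concerns is lack of efficacy. Acting on that can only lower the type I error, and the cost in power depends on how early and how readily one stops: none at a single month-18 look, down to 0.62 in the worst scenario tried. Inflation up to 0.23 requires repeated stopping for benefit at the unadjusted level, which SAP 7 gives no licence for.

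The conclusion rests on three things: that SAP 7 is honoured, that the charter (not among the documents) contains no efficacy stopping rule, and that the sponsor does not end the trial early on unplanned comparative PFS results. A breach of any of these would be a matter of conduct to address when the results are reported. The scenario figures illustrate scale under the assumptions listed and do not predict this trial's error rates.
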